30.0 Recruitment and Advertising

30.1 *From where will subjects be recruited? Check all that apply:

- Outpatients
- Inpatients
- Your Own Patients
- Referrals from Other Physicians
- Hospital or Clinic - Logbooks, schedules, or any other institutional database
- Extramural data or tissue repository or disease database
- Commercial Company
- Advocacy Groups
- Private Practice
- Other

If other, describe.

We have a marketing firm, Dynamic Marketing, that creates social media content to advertise our study on Facebook and Instagram. Dynamic Marketing also utilizes sponsored posts on Facebook and Google Adwords. Every month they write a blog post to create interest and drive traffic to our website. We also utilize our website, flyers; Craigslist, and local newspapers like the San Diego Reader.

30.2 *How will subjects be recruited? Check all that apply:

- Direct contact in a medical setting
- Direct contact in a non-medical setting (explain)
- Newspaper Ad (include publication and date)
- Broadcast media (television/radio/internet)(include details)
- Posted Notice (location(s))
- Dear Valued Patient Letter (use the template located in Help - Click on the '?' icon in the upper right and it appears in the list)
- Newsletters (attach copy or Web site)
- Flyers
- Recruitment Organization(s)
- Dear Colleague Letters
- Social Media
- Other

Provide additional information for any items checked above (if applicable):

See above

30.3 *Do you already have a list of potential subjects for this study?

Yes No

30.4 *Who will do the recruiting? (Check ALL that apply.)

- Investigator
- Study Staff

- Recruiting Agency
- CRO = Clinical Research Organization
- Sponsor
- Other

If other, describe.

30.5 If a patient qualifies for more than one study, how will the Principal Investigator determine which study will be offered to the patient?

Currently there are no competing studies. Should our pending suvorexant study begin and overlap with recruitment for the CORT118335 study, we will alternate enrollment between the 2 studies as they are both under the aims of our P60 alcohol center grant. However, the suvorexant study involves an overnight inpatient stay that may not be possible for some subjects, e.g., due to pet or childcare responsibilities. Thus, we will try to keep enrollment balanced across studies while allowing for subjects' real-world constraints, should there be an overlap in recruitment.

30.6 What limit will be placed on the number of consent forms that a patient will be expected to read and understand at any one time?

There is only 1 consent a subject will be expected to read and understand at any one time.

31.0 Alteration of Informed Consent

31.1 *Are you requesting alteration of the informed consent process?

Yes No

31.2 *Are you requesting permission to waive in-person consent?

Yes No

If Yes, how will informed consent be obtained?

32.0 Consent Procedure

32.1 *Who will conduct the initial informed consent discussion?

(IMPORTANT: Only personnel who have been added to the protocol in iMedRIS/iRIS and have completed the required education in human subjects protections may obtain informed consent.)

[name], MSW or [name], BA, BS

32.2 *Describe the experience and qualifications of the person(s) named above.

[name] has been working in [name] lab as a Study Coordinator since 2017. [name] has been working in [name] lab since 2003.

32.3 *Describe the process of obtaining subjects' consent (Include where, when and how the consent will be obtained).

Subjects are first spoken to on the phone and given a description of the study and a brief

screening to see if they may likely qualify, the subjects that meet basic eligibility requirements and are willing to come in for a screening are given an appointment for their Screening Visit in the laboratory. Subjects will then come in to the laboratory and be given the Informed Consent Form (ICF) to read. They will then be asked if they have any questions about the study. If the subject understands the ICF and agrees to participate, they will sign where appropriate, witnessed by the Study Coordinator, then the Study Coordinator will sign the ICF as well.

32.4 *Describe the method of documenting that informed consent was obtained.

Documentation of the ICFs will be by written signature on the ICF and it is also recorded in the Visit 1 progress note. ICFs will be kept in a separate binder in a locked cabinet in a locked room.

32.5 *List any and all consent/assent forms that will be used.

1 consent form will be used (attached)

32.6 *Have the consent/assent forms been previously approved by a Non-Scripps IRB?

Yes No

If Yes, which Non-Scripps IRB? (Including commercial/academic IRBs)

32.7 *How do you plan to inform subjects of new information that might affect their willingness to continue in the study?

If new information emerges that might affect a subject's willingness to continue in the study, we will incorporate the new information in an addendum to the original consent form for enrolled subjects and also submit a revised consent form for new subjects containing the new information.

(NOTE: We suggest that new information be incorporated into a simple addendum to the original consent form for enrolled subjects and a revised consent form for new subjects.)

32.8 If the study involves minors, describe the process of parental permission and how the assent of the minor will be sought.

The study does not involve minors.

32.9 *Will non-English speaking people be approached to participate in this study?

Yes No

32.10 If you need written HIPAA authorizations from subjects, these documents must be retained for at least 6 years.

Note: If research is conducted in a Scripps hospital, a copy of the consent form, including the Authorization, must be filed in the subject's hospital medical record.

*Check which of the following 3 methods you will use:

- Retain the entire consent form for 6 years
- Retain the Authorization separately for 6 years
- Copy the HIPAA Authorization page and send it to Health Information Services
- Not Applicable

33.0 Waiver of Privacy Rule Authorization

33.1 *Are you requesting to waive individual Privacy Rule authorization?

Yes No

34.0 Risks and Benefits

34.1

*Describe all potential risks of participating in the study, *in simple terms*.

Please include :

- Risks to the subject's privacy and the confidentiality of data.
- The likelihood and seriousness of the most important risks. (Use %, if available, or range, such as 'likely', 'rare', etc.)
- If serious risks are involved, explain which risks are expected to be temporary and which might be permanent.
- Include the possible consequences of serious risks and possible treatment, if known.

Subjects may experience fatigue or distress due to clinical evaluation by rating scales: increased urge to drink or feelings of depression or anxiety following cue exposure procedures.

Subjects may feel pain or discomfort during blood draws when the needle pokes their skin. There may be bruising, swelling, pain or infection later at the puncture site, although this is unlikely. Dizziness and fainting are possible, but very unlikely.

Abnormal test results may cause subjects to experience anxiety and seek additional medical services, and therefore be a potential risk of their research participation.

Medication Side Effects:

Given the small number of subjects studied, no adverse events specific to CORT118335 have been identified.

However, we have given extensive thought and consideration to the safety of CORT118335, a GR/MR antagonist, in subjects with AUD. There is no evidence of similar drugs having abuse potential or alcohol X drug interaction effects on psychomotor coordination or cognitive functioning. We base our conclusions about safety on our own experiences with mifepristone, a GR antagonist, in two studies involving a total of 156 subjects with AUD. In our first study, a human lab study involving 53 non treatment-seeking participants with AUD of moderate or greater severity (AUD-MS) mifepristone was well tolerated, with no evidence of alcohol X drug interactions or abuse potential, and no serious, severe, or unexpected adverse events or treatment discontinuations due to adverse events (Vendruscolo *et al.*, 2015). Similarly, in our recently completed clinical trial of 103 treatment-seeking outpatients with AUD-MS, 1-week of treatment with mifepristone was well tolerate, with headache (Mif=19.7%, placebo=12.5%) and fatigue (Mif=7.0%, placebo=12.5%) the only adverse events reported during treatment in $\geq 5\%$ of subjects. Only one adverse event, headache, was rated as severe, and it resulted in study discontinuation in Week 5 of counseling, i.e., 4 weeks after the last dose of mifepristone, and it was rated as unrelated to study drug (mifepristone 1200 mg). One other subject discontinued treatment on Day 3 complaining of moderately severe nausea, sweating, loss of concentration and depression that was rated as possibly drug-related (mifepristone 600 mg). One SAE occurred that was rated as unrelated to study drug; a subject fell off a horse and was hospitalized 50 days after the last dose administration. Other than significant improvement in GGT and ALT in mifepristone-treated subjects, there were no treatment-related changes in ECG, lab values or vital signs.

Spironolactone is an aldosterone/MR antagonist that has been FDA-approved since 1960 for cardiovascular indications; the most common adverse reaction is gynecomastia after 1 or more months of chronic treatment. Spironolactone has been widely used in veterans with AUD with no safety concerns specific to AUD noted (Farokhnia *et al.*, RSA 2020, attached with permission).

Taken together, the ability of CORT118335 to antagonize GR, and also possibly MR, combined with the preclinical and clinical safety and efficacy found in studies of GR and MR antagonists in AUD, lend support to the safety and potential efficacy of a proof-of-concept evaluation of the GR/MR antagonist, CORT118335, as a novel treatment for AUD.

CORT118335 may cause excessive glucocorticoid or mineralocorticoid receptor antagonism.

Subjects will be told in the informed consent form to notify their doctor or study physician right away if they have the following symptoms:

- * Unusual tiredness or weakness
- * Nausea and/or vomiting
- * Dizziness when standing
- * Aches and pains
- * Loss of appetite and weight loss
- * Dehydration
- * Diarrhea
- * Feeling depressed

Subjects will be given a wallet card to keep with them, to identify the potential risk of excessive glucocorticoid and mineralocorticoid receptor antagonism and potential need for hydrocortisone in the settings of shock or surgery. The card will also contain contact information for the study physician.

Subjects will be cautioned about operating machinery, including automobiles, until they are certain that taking CORT118335 does not affect their ability to drive or work with machinery.

34.2 *Will radiation or radioactive substances be used in your research? For more information on Radiation Safety, move your mouse over the help bubble to the right and click on the link that pops up.

Yes No

If Yes, have you submitted the Protocol and Informed Consent form to the Radiation Safety Committee Officer?

Yes No

If NO, be advised that you must submit to the Radiation Safety Committee Officer.

34.3 Describe any use of radiation, including X-rays, fluoroscopy, radioisotopes or protons. Protocols that include any research use of radiation, radioisotopes or protons must be submitted to the Radiation Safety Committee for review.

34.4 *Does the research protocol involve the use of designated HAZARDOUS CHEMICALS in the clinical setting?

Yes No

List chemical(s) requiring review.

34.5 Describe procedures for minimizing any potential risks, including risks to confidentiality, and assess their likely effectiveness.

Investigators and research personnel are trained in ethical standards for human research and are current with IRB requirements for training and certification. To ensure that all research activities are in full compliance with IRB standards, [name] chairs a weekly meeting with the research team to provide oversight regarding recruitment, research procedures and the clinical status of all active subjects.

Protections Against Risk

CORT118335 will be administered according to a protocol reviewed for safety by the FDA and cross-referenced under Concept's IND #142502. Subjects will be advised to avoid driving or performing hazardous tasks until they know how they will react to the medication, and to not take any herbal, over-the-counter or prescribed drugs unless approved by the study physician. The 900 mg daily dosage is currently under study for non-alcoholic liver disease and anti-psychotic-induced weight gain. Dosing regimens and durations were chosen to provide the minimum total duration of drug exposure that is still compatible with achieving optimal drug effects and maintaining subject safety.

Importantly, the research group has a well-established record of patient safety in the conduct of similar human laboratory studies and pharmacological trials. CORT118335 is considered safe when used in accordance with the procedures to be employed in the study and exposure to drug is of brief duration i.e., 2 weeks of administration. Subjects with any conditions which would represent increased risk, e.g. significant medical or psychiatric disorders or pregnancy, will not be admitted to the study. Stringent procedures will be followed to minimize the risk of adverse reactions. These include the following: 1.) a medical history; 2.) a physical exam, including EKG, blood chemistry, complete blood count (CBC), liver function tests (LFT's), urinalysis, and urine toxicology screen for drug of abuse; 3.) a menstrual history, negative pregnancy test prior to study admission, and birth control will be documented in women of childbearing potential, to avoid giving suvorexant to women with unrecognized pregnancies; 4.) Women of child bearing potential will be advised to use an effective method of birth control for study duration and for 1 week thereafter; 5.) and close medical supervision. Any clinically significant abnormalities persisting at the end of the study will be followed by the investigator until resolution or until a clinically stable endpoint is reached. The clinical ratings and blood tests will be performed by experienced personnel to minimize complications and unnecessary fatigue and distress.

All subjects are required to be abstinent a minimum of 3 days prior to the lab session. Depending upon the extent of alcohol use and individual tolerance some subjects may be at risk for alcohol withdrawal. To protect against these risks each subject will be carefully evaluated with the CIWA by an experienced study clinician at the randomization visit for potential withdrawal risk and symptoms, including vital signs, time of last drink, quantity consumed, pattern of drinking, and history of alcohol withdrawal. In the unlikely event that significant (CIWA > 9) withdrawal symptoms are present, subjects will not proceed with the study and will be referred to a nearby detox facility.

Subjects may benefit directly from study medications, evaluation of their medical status, and study participation. Prior follow-up of non-treatment-seeking subjects in our human lab studies with alcohol use disorder have shown no harmful effect and increased likelihood of entering treatment following participation. During the course of the study, subject care will be supervised by a physician. Medical and laboratory examinations will be conducted prior to drug administration or at any time the subject develops adverse reactions. Subjects are provided with phone numbers to call for 24/7 medical attention. Any subject who develops side effects or medical complications that cannot be satisfactorily treated within the parameters of the research protocol will be discontinued from the study and referred for the most appropriate medical care.

Confidentiality will be preserved by the following measures: keeping the subject case report forms (CRF) in locked cabinets; CRF's and computerized data will be identified by numerical code so that neither the subject's name will not be used; no information will be released to non-study personnel regarding the identity or progress of subjects without written request by the individual subject to the Principal Investigator. A Certificate of Confidentiality will be obtained to protect against involuntary disclosure of the identities of research participants.

34.6 What provisions have been made for ensuring that medical or professional intervention is available to subjects if an adverse event occurs?

Every effort will be made to minimize the risk of clinical deterioration. The subjects will be closely monitored. Highly trained and experienced personnel will provide a degree of supervision that may not be available under usual treatment conditions. A study physician is available 24 hours a day, 7 days per week in the case of clinically significant adverse events. The study physician will evaluate any subject experiencing clinical deterioration and make a clinically-based decision regarding study discontinuation and referral for appropriate care in consultation with the P.I.

34.7 *Is there potential for direct benefit to the subject?

Yes No

If yes, describe.

Subjects may benefit directly from study medication, evaluation of their medical status, and study participation.

34.8 *Will there be benefit to the class of subjects or to society?

Yes No

If yes, describe.

Alcohol use disorder is a chronic relapsing disorder characterized by repeating cycles of pathological alcohol use, acute withdrawal, and protracted abstinence. The cost to society is enormous with estimates in excess of 220 billion dollars per year related to medical costs, lost productivity, and premature death. To date, 3 medications have FDA approval for alcohol use disorder, disulfiram, naltrexone, and acamprosate. However, all current drugs for alcohol use disorder are underutilized and have modest effect sizes, underscoring the critical need for the development of pharmacotherapies with larger effect sizes to move the alcohol use disorder treatment field forward.

We anticipate that subjects with an alcohol use disorder that are treated with CORT118335 will report significantly decreased craving for alcohol following alcohol cue exposure in the laboratory and report fewer symptoms of protracted abstinence (e.g., craving, relapse to drinking, mood and sleep disturbances) under naturalistic conditions, relative to those treated with placebo. This will allow future development of CORT118335 as a potential treatment option for alcohol use disorder, which will benefit society as a whole.

34.9 *Describe why you think the risks to subjects are reasonable in relation to the anticipated benefits?

The risks to subjects are reasonable in relation to the anticipated benefits because all measures will be taken to minimize risks to research participants. The health and safety risks associated with being a research subject are far out weighted by the potential direct benefit of reducing heavy alcohol consumption and contributing to research that may reduce alcohol use disorder in society.

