21.0 Medical Devices

21.1 *Does your study involve the use of any medical devices?

Yes No

22.0

Alternative Treatments

22.1 *Are there alternative drug(s), device(s) or procedure(s) that are approved for use in the United States?

Yes No

If Yes, describe:

Acamprosate, naltrexone and disulfiram

22.2 *Is the study drug/device/procedure currently available without participating in the study?

Yes No

If Yes, describe:

23.0

Data and Safety Monitoring

23.1 *Describe the plan for monitoring data and safety. (A plan is REQUIRED.)

Stringent procedures will be followed to minimize the risk of adverse reactions, including the following:

- Subjects will be excluded who are at increased risk as determined by the study physicians, [name], PhD, and [name], based on a thorough medical history, physical exam, ECG, comprehensive metabolic panel (CMP) that includes potassium levels, complete blood count (CBC), liver function tests (LFT's), urinalysis, and urine toxicology screen for drug of abuse (UDS). Subjects with any conditions that would expose them to unusual risk (e.g., significant medical disorders or pregnancy) will be excluded. The CMP, CBC, LFT's, urinalysis, UDS, ECG and vital signs also will be obtained after the last dose administration.
- Subjects will be carefully monitored by the P.I. and [name]., PharmD, our independent Medical Safety Monitor, during weekly laboratory meetings with all personnel involved in the study.
- A menstrual history, negative pregnancy tests, and birth control will be documented in women to avoid giving study drugs to women with unrecognized pregnancies.
- All subjects of childbearing potential and their opposite sex partners will be required to use a double barrier form of birth control for the duration of the study and for one month thereafter.
- Subjects will be instructed to carry a wallet card at all times identifying the potential risk for excessive glucocorticoid receptor antagonism and excessive mineralocorticoid receptor antagonism and potential need for hydrocortisone in the settings of shock or surgery. The card will also contain contact information for the P.I. and study physician.
- Subjects will be advised neither to drive a car nor operate complex machinery until they have gained sufficient experience on drug to gauge whether or not it affects their mental and/or motor performance adversely.

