37.10 Inclusion Criteria

*Use the link below to add inclusion criteria.

Order Number	Criteria
1	
 • Male or female volunteers, 18-75 years of age. • Meets DSM-5 criteria for current alcohol use disorder of moderate or greater severity (AUD-MS, ≥ 4 symptoms). • In the month prior to screening, reports drinking ≥ 21 standard drinks per week if male, ≥ 14 if female, with at least one heavy drinking day (≥ 5 drinks/d if male, ≥ 4 drinks/d if female) per week. • Subjects will be non treatment-seekers because the study is not a treatment trial, and to avoid exposing treatment-seekers to alcohol cues. • Subjects must be abstinent a minimum of 3 days (but not more than 7 days) prior to the alcohol cue reactivity lab session. • Negative BAC and EtG/EtS and a CIWA score of ≤ 9 at the time of the lab session. • In acceptable health in the judgment of the study physician, on the basis of interview, medical history, physical exam, ECG, routine urine and blood chemistry. • Females with childbearing potential must have a negative pregnancy test on the screening and randomization visits. • All subjects must agree to use double barrier contraception for the duration of the study and one month thereafter, i.e., males must use condoms and females must use spermicide and/or a non hormonal barrier method, and their opposite sex partner must likewise use an effective non hormonal form of contraception. • Able to provide informed consent and understand questionnaires and study procedures in English. • Willing to comply with the provisions of the protocol and take oral medication.

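### The protocol gives conflicting contraception requirements: double barrier until one month after the study in 23.1 and 37.10, any effective method until one week after in 34.5, where the adjacent item names another trial's drug

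*Protocol*

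**What the plan says.** Three sections of the protocol state a contraception rule.

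- **37.10, Inclusion Criteria:** "All subjects must agree to use double barrier contraception for the duration of the study and one month thereafter". The same bullet then explains the term: men use condoms, "females must use spermicide and/or a non hormonal barrier method", and the partner must also use an effective non-hormonal method.
- **23.1, Data and Safety Monitoring:** "All subjects of childbearing potential and their opposite sex partners will be required to use a double barrier form of birth control", with the same period, "double barrier form of birth control for the duration of the study and for one month thereafter".
- **34.5, Protections Against Risk:** "Women of child bearing potential will be advised to use an effective method of birth control for study duration and for 1 week thereafter". This is item 4 of a numbered list of risk-reducing procedures. Item 3, on menstrual history, pregnancy testing and birth control, gives its purpose as "to avoid giving suvorexant to women with unrecognized pregnancies".

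The trial drug is CORT118335, later renamed miricorilant. Suvorexant appears in one other place, section 30.5, as the drug of a different study: "Should our pending suvorexant study begin and overlap with recruitment for the CORT118335 study". The parallel sentence on unrecognized pregnancy in 23.1 refers to study drugs in general and does not name suvorexant.

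**The concern.** All three passages are written as rules to be applied, and the protocol does not say which governs. A staff member who relies on 34.5 would tell a woman that any effective method is enough and that she may stop one week after the study. She could follow that advice exactly, for instance with a hormonal method, and still fall short of what 37.10 required her to agree to at entry.

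At stake is possible pregnancy exposure to an investigational drug. Section 34.1 acknowledges that few people have taken it so far. The last pregnancy check described in 28.1 is an at-home test in Week 4, reviewed at the virtual follow-up two weeks after dosing stops. If the study ends at that visit, the period on which the sections disagree falls after the last scheduled contact. Compliance then depends on the instruction the participant was given.

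The suvorexant reference suggests that this part of 34.5 came from another protocol. If so, the contraception item beside it may not have been written for this drug.

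**Working it through.** No sample size, power or error rate is involved. The check is a comparison of the texts and a short calculation of the periods.

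**Side by side**

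| | 37.10 | 23.1 | 34.5 |
|---|---|---|---|
| Who is named | All subjects, plus opposite-sex partner | Subjects of childbearing potential, plus opposite-sex partners | Women of childbearing potential |
| Method | Double barrier, explained as non-hormonal | Double barrier | Any effective method |
| Period after the study | One month | One month | One week |
| Force | Must agree, as a condition of entry | Required | Advised |

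Section 34.5 differs from both other sections on every row. Sections 23.1 and 37.10 agree on period and force but not fully on coverage (subjects of childbearing potential against all subjects). The explanation in 37.10 also allows spermicide and/or a barrier for women, which is not obviously the same as the double barrier it is meant to explain.

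**Periods after the study**

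- 34.5: 1 week = 7 days.
- 23.1 and 37.10: one month = 28 to 31 days (assumed range for a month).
- Gap: 28 − 7 = 21 days to 31 − 7 = 24 days.
- Ratio: 28 / 7 = 4.0 to 31 / 7 = 4.4.

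**Periods after the last dose**

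Section 28.1 puts the follow-up visit 2 weeks after the cue session and the end of dosing. I found no definition of when the study ends for a participant. Assume that it ends at that visit:

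- 34.5: 14 + 7 = 21 days.
- 23.1 and 37.10: 14 + 28 = 42 to 14 + 31 = 45 days.
- Ratio: 42 / 21 = 2.0 to 45 / 21 = 2.1.

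If the study were instead taken to end with the last dose, the 7 against 28 to 31 days above would apply directly. The ratio depends on this reading; the gap of 21 to 24 days does not.

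**Is this only superseded text?** The amendment summary covers exclusions, stopping criteria, drug packaging, extra blood draws, the drug's name, a questionnaire and recruitment. It describes no contraception change, and it characterises the 13 further amendments as advertising and administrative. All three rules stand in the body of the application, so this is not a difference between an amendment log and current text.

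**The case against.** The strongest reply is that the entry criterion governs in practice. Nobody can be enrolled without agreeing to 37.10, whatever 34.5 says, and 34.5 is a narrative answer on an ethics application form. Participants see the consent form and study instructions, which are not available for this review. The rules can also be read as nested: a woman who keeps to 37.10 has in effect kept to 34.5, and silence about men and partners is an omission rather than a contradiction. Pregnancy is excluded, it is tested for at screening and randomization, and a Week 4 test is reviewed. Finally, the text is Version 1.0 of the application and plainly predates some amendments: 27.1 still shows the $500 payment total that was later raised to $575.

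Part of this stands. What participants were told cannot be checked, and confusion among staff is possible but not shown. The four-fold ratio applies only to the post-study period. The pregnancy tests are real safeguards, though none is described after Week 4. That the text was carried over from the suvorexant study is an inference; the protocol does not say so, and the same part of 34.5 also names CORT118335.

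The reply does not remove the conflict. Nesting works in one direction only: following 34.5 does not satisfy 37.10. One week and one month are different numbers, so 34.5 cannot be a shortened form of the other rule. The protocol gives no order of precedence, 34.5 is worded as something staff will tell women, and no listed amendment repairs it. The wrong drug name is an error whatever its origin.

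**Conclusion.** The concern holds. Section 34.5 contradicts 23.1 and 37.10 on the length of contraception after the study, by 21 to 24 days. It also sets a looser method, names fewer people and advises rather than requires. The relative size is about four-fold after the study, or about two-fold after the last dose if the study ends at the two-week follow-up visit. Both ratios take a month as 28 to 31 days.

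The one-week rule bears on every woman of childbearing potential among the planned 50 participants; under 37.10 the requirement reaches all participants and their opposite-sex partners. The protocol does not give the number of women expected.

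This is an internal inconsistency in a participant-protection rule. It does not touch the endpoint, sample size or analysis, but it should be corrected because staff need one unambiguous instruction. This review takes no position on which rule is right.

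**What to change.** Reconcile 23.1, 34.5 and 37.10 so that each carries the same statement of:

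- who is covered, including whether men and partners are;
- which methods are acceptable, including how double barrier is to be understood in 37.10;
- how long contraception continues, counted from a named event such as the last dose or the last visit;
- whether it is an obligation or advice.

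The sponsor and study physicians must decide the content. Check the consent form, study instructions and any other participant material against the agreed statement. Replace suvorexant in 34.5 with this trial's drug, and read the rest of that list for other text that may belong to another study.

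The cost is a wording amendment through the IRB, with no change to sample size, visits or analysis. If the consent form proves to differ from the agreed statement, it would need correcting too, and anyone still within the affected period would need to be told.
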